- 2) The fake (placebo) Erchonia® HLS is designed to have the same physical appearance as the actual Erchonia® HLS, including the appearance of any visible light output, and neither the active nor the placebo lasers put out any notable degree of heat or noise. Therefore, there are no distinguishing factors between the active and placebo lasers for subjects or investigators. Additional information on the design, application and proven ineffectiveness of the placebo HLS Laser Device to be used in this study is contained above on pages 10-11 of this protocol document under the section titled: PLACEBO DEVICE INFORMATION.
- 3) There will be two independent investigators interacting with subjects: (i) *administration investigator*: who will be responsible for administering the study treatments; (ii) *assessment investigator*: who will be responsible for recording the study outcome measures. Only the administration investigator will be aware of whether a subject is assigned to Treatment Group A or B, although he or she will not be made aware of whether A or B corresponds to the true or fake laser. Neither the assessment investigator nor the subject will be aware of the subject's A/B Group assignment. In this way, the assessment investigator will not be able to form an association between A/B Treatment Group and active/sham device over the course of the study if a treatment effect is observed.
- 4) During the laser procedures, both the subject and the administration investigator will wear safety glasses that filter out the laser light spectrum. The administration investigator will wear KenTek Corporation KenTek C22-KMT-6101 light blue safety glasses and the subject will wear KenTek Corporation KGOG-6101 light blue Medium Goggles safety goggles. Additional information on this safety eyewear is contained above on pages 6-8 under the section titled: DEVICE SAFETY: RISK AND PREVENTION OF EYE INJURY.

TREATMENT GROUP RANDOMIZATION

Subject allocation to treatment group (A or B) will be via a randomized block design with varying block sizes of two, four and six subjects. In each block, one-half of the subjects will be randomly assigned to Group A and the other half will be randomly assigned to Group B.

Randomization will be attained using computer generation sequence methodology, insuring that the randomization methodology and the generated allocation sequence is concealed from the investigator and subjects.

Concealment will be insured as follows:

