5. An individual for whom the caregiver decides not to permit participation in the study will continue to work with the physician on the ASD treatment plan goals for the minor patient.

Compensation

A subject or his or her caregiver(s) will not be offered money or any other form of compensation to participate in the clinical study; however, there will also not be any charge for the cost of the study treatments with the Erchonia® HLS laser device or for the cost of any other directly-related evaluations or measurements that occur as part of the subject's participation in this study.

Subject Sample Size

There will be 40 qualified subjects enrolled in this clinical study:

- 20 subjects in the test group
- 20 subjects in the control group

Rationale and Justification for Sample Size

This study is powered to compare one active arm with placebo. Sample size calculation is based on the primary efficacy measure of the mean change from study baseline to endpoint (end of the 4-week treatment period) in the Aberrant Behavior Checklist (ABC) Irritability Subscale score adjusted for the baseline ABC Irritability Subscale score.

Based on detecting a mean difference of -8.5 points between test and placebo groups in the change in ABC Irritability Subscale score adjusted for the baseline ABC Irritability Subscale score being considered clinically relevant with a SD of 8.9, a two-sided test with 80% power and a 5% level of significance, the number of subjects needed per treatment group is 18.

From here, it is anticipated that about one-tenth of subjects overall may withdraw or be terminated from the study prior to completion for various reasons. Therefore, the following formula is used to determine the final needed starting sample size for each procedure arm:

Final sample size = sample size X $1/(1-d)$; where $d = \# \text{ expected dropouts}/\# \text{ subjects enrolled}$.

Final sample size = $18 \times 1/(1-0.11)$; where $d = 2/19$

Final sample size = $18 \times 1/0.89 = 18 \times 1.124 = 20$ subjects per treatment group.

Therefore, a minimum starting sample size of 20 subjects in each treatment group (40 subjects in total) is needed to ensure that a sufficient number remains at study endpoint (18 evaluable subjects per treatment group) for any significant differences found between treatment groups to be considered statistically valid and representative of the general population being sampled.

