- Mean change from baseline to endpoint in the other 4 ABC Subscale scores, based on ratings by the subject's primary caregiver:
 - ✓ Lethargy/Social Withdrawal
 - ✓ Stereotypic Behavior
 - ✓ Hyperactivity/Noncompliance
 - ✓ Inappropriate Speech
- Mean change from baseline to endpoint in the global ABC score
- Change in ratings on the CGI-S from baseline to study endpoint evaluation
- Change in ratings on the CGI-I from baseline to study endpoint evaluation

STATISTICAL METHODS

Efficacy analysis will be according to the intent to treat (ITT) principle by last observation carried forward (LOCF).

Intent to Treat: Subjects will be included in the ITT analysis if they complete their baseline clinical assessments and had at least one post-randomization efficacy evaluation and corresponding baseline value.

Last observation carried forward (LOCF): Missing data will be handled by carrying forward the last observation for the relevant measure. The LOCF data set included data recorded at a given time point, or, if no observation was recorded at that time point, data carried forward from the previous time point with available data. Baseline data will not be carried forward or averaged to impute missing values for the LOCF data set.

STATISTICAL ANALYSIS

Primary Efficacy Analysis

For the continuous primary efficacy measure of ABC Irritability Subscale score, change scores will be evaluated by analysis of covariance (ANCOVA). The ANCOVA models for LOCF data sets will include the baseline measure as a covariate and treatment (active of placebo) as main effects.

Secondary Measures Analysis

- For the continuous secondary efficacy measures of the other 4 ABC Subscale scores, and the Global Score, change scores will be evaluated by analysis of covariance (ANCOVA). The ANCOVA models for LOCF data sets will include the baseline measure as a covariate and treatment (active of placebo) as main effects. A two-way significance level of 5% will be considered to be statistically significant.

- For the categorical measures of the CGI will be analyzed within the framework of the generalized Cochran-Mantel Haenszel (CMH) procedure.
- Responder rate will be evaluated using Fisher's exact test to compare the proportion of responder rates between the test and control groups.

P-values will be 2-tailed tests of significance rounded to 3 decimal places. All analyses will be performed at the 5% significance level.

SAFETY ANALYSES

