Safety analyses will be completed on all subjects who were randomized to treatment group and received at least the first study treatment administration with the Erchonia® HLS Laser device.

Safety will be assessed by evaluating and comparing frequency and incidence of observed and/or reported adverse events between test and placebo treatment groups. A chi-square test with a continuity correction will be performed to compare the percentage of subjects who had adverse events and/or reactions between the test and placebo group subjects.

SAFETY AND CONFIDENTIALITY ISSUES

ADVERSE EVENTS

At any time throughout the study, any adverse event reported by a subject and/or subject's caregiver and/or observed by the study investigator will be recorded on the case report form and subsequently evaluated by the Principal Investigator for its relation to the study treatment and whether or not any corrective action need be taken. All applicable adverse events will be reported to the IRB.

Formal evaluation of the occurrence of any adverse events will take place at the end of each study treatment administration and each evaluation visit. In addition, subjects/caregivers will be instructed to contact the investigator at any other time that he or she believes a potential adverse event has occurred during the course of the subject's participation in the clinical study.

The investigator will record the observation or report of any adverse event and assign the relationship to the study treatment on the appropriate case report form in the subject's file and will report the occurrence to the governing IRB, if and as appropriate, within 5 days of the reported occurrence, or within 24 hours in the occurrence of a serious adverse event including death.

The only known potential adverse event associated with the use of laser devices is that long-term exposure to laser light could cause damage to eyesight. As a precaution, during all laser treatment administrations with the Erchonia® HLS at the test site, both the subject and the administration investigator will wear safety glasses that filter out the laser light spectrum. The administration investigator will wear KenTek Corporation KenTek C22-KMT-6101 light blue safety glasses and the subject will wear KenTek Corporation KGOG-6101 light blue Medium Goggles safety goggles. Additional information on this safety eyewear is contained above on pages 6-8 under the section titled: DEVICE SAFETY: RISK AND PREVENTION OF EYE INJURY.

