There are no other known potential adverse events from application of the study lasers. There have been no observed or reported adverse events or reactions to the application of the family of Erchonia® laser devices in several other studies using these laser devices. However, potential adverse events that may occur include, but are not necessarily limited to: skin irritation, skin discoloring, skin rash, skin indentations and infection. There may also be unknown or unanticipated risks to using the laser devices with this study treatment.

MONITORING OF THE CLINICAL STUDY

The study Monitor will assure that the investigator is executing the protocol as outlined and intended. This includes insuring that a signed informed consent form has been attained from each subject's caregiver prior to commencing the protocol, that the study procedure protocol is administered as specified, and that all study evaluations and measurements are taken using the specified methods and correctly and fully recorded on the appropriate clinical case report forms.

SUBJECT PRIVACY AND CONFIDENTIALITY

Records for each subject in the study will be maintained in separate files in a locked filing cabinet at the test site. The Principal Investigator will be responsible for ensuring that all records for a subject are stored in that subject's file at all times other than when information is being recorded on them.

Once a subject's participation in the study is complete and all of the required records are in the subject's file, copies of the documents may be made and supplied to the study Sponsor who will store them in a locked filing cabinet. Copies of subjects' case report forms will also be sent to Regulatory Insight, Inc. for the purpose of monitoring the data collection process and analysis of results. Regulatory Insight, Inc. will also maintain these copies in a separate clinical study file that is kept in a locked filing cabinet. The original records will be maintained at the test sites upon completion of the study in their original files and stored in a locked filing cabinet.

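### The only planned adverse-event test is a continuity-corrected chi-square with about 20 per arm and no sparse-table fallback; Fisher's exact test with exact intervals would be a free, minor improvement

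*Combined protocol and SAP*

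**What the plan says.** Under Safety Analyses, the analysis set is defined as follows: "Safety analyses will be completed on all subjects who were randomized to treatment group and received at least the first study treatment administration". The section then says that the frequency and incidence of adverse events will be evaluated and compared between arms, and gives one test: "A chi-square test with a continuity correction will be performed to compare the percentage of subjects who had adverse events". It names no alternative for small expected counts, no rule for a table without events, and no confidence interval.

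The sample size section sets "20 subjects in the test group" and "20 subjects in the control group". Allocation is equal within blocks: "In each block, one-half of the subjects will be randomly assigned to Group A". The Statistical Analysis section says "P-values will be 2-tailed tests of significance rounded to 3 decimal places" and sets a 5% level for all analyses. For the responder rate, the other two-group binary comparison, the same section uses Fisher's "exact test to compare the proportion of responder rates between the test and control groups".

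On expected events, the Adverse Events section says "There have been no observed or reported adverse events or reactions to the application of the family of Erchonia® laser devices" in several other studies. It then lists skin reactions and infection as possible events and allows for unknown risks. It gives no numerical rate.

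**The concern.** With 40 subjects and a history of no reported events, the table of subjects with and without an adverse event may well be sparse. At 20 v 20, fewer than 10 affected subjects in total puts an expected count below 5, where the chi-square approximation is weak. With no affected subjects the statistic does not exist, so the prespecified test returns nothing for the very outcome that the sponsor's history points to.

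An excess on active with few or no events on placebo is the safety pattern of most interest. If another test at the same level reaches significance in some such tables and never does worse, there is no reason to prefer the planned one, and the plan already names that other test for responders. A p-value from either test also says little about which event rates the data can exclude, and the section plans no interval.

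**Working it through.** **Inputs.** Arm sizes of 20 and 20 (Subject Sample Size); two-sided 5% (Statistical Analysis); continuity-corrected chi-square (Safety Analyses). The documents give no event rate, power or sample size for the safety comparison.

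**The plan's own figure.** The arm size comes from the primary endpoint: difference 8.5, SD 8.9, 80% power, two-sided 5%. The normal-approximation formula gives 2 × (1.960 + 0.842)² × (8.9/8.5)² = 17.2, so 18 per arm, as stated. Dividing by 0.89 gives 20.2, which the plan takes as 20. This fixes the size of the safety table.

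**Planned statistic.** With a and b the subjects with and without an event on active, and c and d the same on placebo:

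X² = N(|ad − bc| − N/2)² / (r1 × r2 × c1 × c2), on 1 df, where r1 and r2 are the arm totals and c1 and c2 the totals with and without an event.

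For x events v 0 at 20 v 20 this reduces to X² = 40(x − 1)² / [x(40 − x)].

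**Fisher's exact test.** For x v 0 in equal arms the two-sided p-value is 2 × C(20, x) / C(40, x).

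| Table, 20 v 20 | X² | Planned p | Fisher p |
|---|---|---|---|
| 0 v 0 | none | none | 1.000 |
| 2 v 0 | 0.526 | 0.468 | 0.487 |
| 3 v 0 | 1.441 | 0.230 | 0.231 |
| 4 v 0 | 2.500 | 0.114 | 0.106 |
| 5 v 0 | 3.657 | 0.056 | 0.047 |
| 6 v 0 | 4.902 | 0.027 | 0.020 |

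For 5 v 0, X² = 40 × 16 / (5 × 35) = 3.657 and Fisher p = 2 × 15504 / 658008 = 0.047. The smallest expected count is 20 × 5/40 = 2.5. For 0 v 0, c1 = 0, so the denominator is zero.

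**All tables.** There are 21 × 21 = 441 tables at 20 v 20. Fisher is significant in 214 and the planned test in 206. The 8 discordant tables are 5 v 0 and 11 v 4 with their mirror images (arms exchanged, or events and non-events exchanged). In all 8 only Fisher is significant. The 11 v 4 case is almost a tie: X² = 40 × (140 − 20)² / (20 × 20 × 15 × 25) = 3.840 against a critical value of 3.841, which is p = 0.050 after rounding, with Fisher at 0.048.

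**Arm sizes other than 20 v 20, for 5 v 0 (planned p).** 19 v 19: 0.055 (Fisher 0.046). 18 v 18: 0.054 (Fisher 0.045). 5/19 v 0/20: 0.048. 5/20 v 0/19: 0.064.

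**Power under assumed event rates (not in the documents), Fisher v planned.** 25% v 0%: 0.59 v 0.38. 25% v 1%: 0.51 v 0.35. 25% v 5%: 0.30 v 0.23. 40% v 5%: 0.72 v 0.69. With equal rates in both arms, Fisher's exact type I error is about 1.2% at a rate of 10% and 2.5% at 30%, so it stays well inside 5%.

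**Chance of an empty table.** At an assumed common rate of 0.5%, 1%, 2% or 5%, the chance of no affected subject in 40 is (1 − rate)⁴⁰ = 82%, 67%, 45% or 13%.

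**What no events would exclude.** For 0/20 the exact two-sided 95% upper limit is 1 − 0.025^(1/20) = 16.8%.

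**The case against.** The case against giving this weight is strong, and most of it stands.

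- A reader might infer that the plan has nothing to say about safety if no events occur. It does: the section also compares frequency and incidence, so 0/20 v 0/20 would be reported, and a 5 v 0 excess would be visible whatever its p-value.
- A reader might infer that the planned test is less sensitive in sparse tables generally. It is not: at 2 v 0 and 3 v 0 its p-value is slightly the smaller, and neither test is significant at 4 v 0 or fewer. Among x v 0 tables only 5 v 0 changes verdict, and that needs events in 25% of the active arm, which sits awkwardly with an expectation of almost none.
- The 5 v 0 result needs near-equal arms. Subjects are randomized before the qualification evaluation, and the safety set counts only those treated, so imbalance is possible. At 5/19 v 0/20 the planned test is significant.
- The change of test does not by itself help when no events occur: Fisher returns 1.000, and the 16.8% limit comes from the arm size under either test.
- A near-zero rate is an inference. Any event is recorded at every treatment and evaluation visit, and with 10 to 30 affected subjects at 20 v 20 all expected counts are at least 5.
- Nothing in the documents says that a missing or non-significant p-value will be taken as proof of safety.

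What the objection does not remove: the statistic is undefined for an empty table, no fallback is written, and no table at 20 v 20 favours the planned test at 5%.

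**Conclusion.** The point holds as a minor improvement. At 20 v 20 the planned test never reaches 5% when Fisher's exact test does not, loses to it in 8 of 441 tables, and cannot be computed without events. The 5/20 v 0/20 example (0.056 against 0.047) is a single borderline table, not evidence of a general loss of sensitivity, and it rests on arms of equal or nearly equal size. That sparse tables are likely rests on the sponsor's reported history; the event rates used above for power and for empty tables are assumptions. Study success rests on the primary endpoint alone, so no success decision changes. The more useful part of the change is the intervals, because neither p-value shows how high an event rate remains compatible with the data.

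**What to change.** In Safety Analyses, replace the continuity-corrected chi-square with Fisher's exact test, two-sided at 5%, as already specified for responders. Report the proportion of subjects with any adverse event in each arm with exact 95% limits, and the risk difference with an exact 95% interval. State that if no events occur, only counts and intervals are given.

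Dropping the continuity correction is not a substitute: it gives p = 0.017 for 5 v 0, but with expected counts of 2.5 that figure is unreliable.

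The cost is a sentence or two in the SAP, best written before unblinding. No extra subjects, visits or data are needed.

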- (i) Each computer-generated randomization sequence is unique and will therefore not be able to be replicated.
- (ii) Randomization will occur to either 'Group A' or to 'Group B' rather than to a test or placebo group, and only the designated individual at the study Sponsor's site will know which assignment (A or B) corresponds to the active Erchonia® HLS device and which corresponds to the fake device, with this information not to be revealed until study unblinding that occurs after all data has been entered into the database and the database is sealed prior to statistical analyses.

SUBJECTS

Subjects will be those whose caregivers voluntarily sign the informed consent form, who pass the study qualification evaluation and are subsequently enrolled in the study.

Subject Recruitment

The test site will be responsible for recruitment of its own subjects.

The recruitment process will work as follows:

1. A minor individual has a pre-scheduled appointment at the physician's office (that in the context of this clinical study also functions as the investigator's test site) pertaining to his or her ASD and/or related issues.
2. At the time of this visit, if the physician believes that the patient may satisfy the study qualification criteria (i.e. there are no obvious indicators that may exclude him or her), then the physician will present to the patient's caregiver(s) the option of being a subject in the clinical study.
3. If the patient's caregiver expresses interested in possibly having the minor patient take part in the study, the physician – now in the role of study investigator – will personally review the informed consent form with the individual's caregiver(s) and answer any questions. The individual's caregiver may sign the informed consent form at that visit or he or she may think about it for a while and sign the informed consent form at a later time (taking as long as desired, from hours to days to sign as long as study enrollment is continuing at the time the decision to sign is made), or he or she may refuse to permit the minor child to participate. The Information Sheet for the child/adolescent is also reviewed with the patient, as applicable.
4. Once a caregiver signs the informed consent form, the minor subject will receive a subject ID and proceed to the study qualification evaluation phase of the study.

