The PI will commence by presenting and reviewing in detail the items in the informed consent form with the individual's designated caregiver(s) and answer any questions he or she may have. To proceed, the individual's designated caregiver must willingly sign the informed consent form.

ASSIGNMENT OF SUBJECT IDENTIFICATION NUMBER

The subject will be assigned a unique subject identification number based upon his or her order of entry into the study.

Additional information about the informed consent and subject ID number assignment is contained in a later section of the protocol titled, "SAFETY AND CONFIDENTIALITY ISSUES."

SUBJECT GROUP RANDOMIZATION

Subjects will be randomly assigned to either Treatment Group A or to Treatment Group B, following the methodology outlined above in the STUDY DESIGN section of the protocol.

STUDY QUALIFICATION EVALUATION: INCLUSION/EXCLUSION CRITERIA

The following tools from the Study Test Battery to be used during Study Qualification Evaluation

- Diagnostic and Statistical Manual of Mental Disorders, 4th Edition, Text Revision criteria (DSM-IV-TR)BDI®-II
- Autism Diagnostic Interview (ADI-R)
- Aberrant Behavior Checklist (ABC) Irritability Subscale
- Clinical Global Impressions – Severity (CGI-S) scale

INCLUSION CRITERIA

- Male or female child or adolescent aged 5 to 17 years
- Subject has met Diagnostic and Statistical Manual of Mental Disorders, 4th Edition, Text Revision criteria (DSM-IV-TR) for autistic disorder within the past 2 years, as diagnosed by a trained, qualified medical professional such as a pediatric neurologist, child psychiatrist or developmental pediatrician
- Diagnosis is confirmed by Autism Diagnostic Interview (ADI-R)
- Subject demonstrates 'irritable' behaviors such as tantrums, aggression, self-injurious behavior, or a combination of such behaviors
- Subject's Aberrant Behavior Checklist (ABC) Irritability Subscale score is ≥ 18
- Subject's Clinical Global Impressions – Severity (CGI-S) scale score is ≥ 4 (4=moderately ill)
- Subject's current therapeutic/intervention plan for treating his or her autistic disorder (educational/behavioral or other therapy; medication use; dietary interventions) has been consistent/stable over at least the past 3 months

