Subjects' identities will be kept confidential by assigning each subject a subject ID upon acceptance into the study. The subject ID will comprise the investigator's first and last name initials and a three-digit number that will be determined based upon the subject's order of entry into the study. For example, the eighth subject to be enrolled under Principal Investigator [name] will have a subject ID of MB008. Neither the study Sponsor nor Regulatory Insight, Inc. will receive any additional identifying information about a subject and will therefore have no way of linking a subject ID to a particular subject and his or her results.

INFORMED CONSENT

- Informed consent will be an agreement between the study PI and each subject's designated caregiver, having the capacity to understand and make an informed decision. Consent will be obtained prior to each potential subject's participation in this clinical trial.
- The caregiver for each subject participating in this clinical trial will be made aware of the fact that the subject's participation involves research and the intent of the research, the expected duration of participation and a description of the procedures that will be followed.
- The caregiver for each subject will be made aware of the reasonably expected benefits the subject might receive, as well as any risks or potential discomfort that are involved.
- The caregiver for each subject will be made aware of alternative procedures that are available to the subject.
- The caregiver for each subject will be made aware that the subject's records will remain confidential, but that the FDA and the IRB has the right to inspect those records.
- The caregiver for each subject will be told that the subject's participation in the clinical trial is voluntary, without force or influence from the investigator or sponsor.
- The caregiver for each subject will be given the name and method of contacting the appropriate person(s) to answer any questions about the research and in the event of research-related injury.

The informed consent form can be found in **Appendix B**.

CASE REPORT FORMS

The case report forms that will be used to collect the data from each subject in this clinical trial can be found in **Appendix C**.

TABLE OF SUBJECT EVENTS

The following table provides a progressive summary of subject events throughout the duration of this pivotal trial.

PRE-TREATMENT ACTIVITIES
STUDY QUALIFICATION

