
 ➤ A minor individual who attends the investigator’s office for a pre-scheduled appointment pertaining to his or her ASD and/or ASD-related issues is deemed potentially suitable by the investigator for participation in the clinical study. ➤ The investigator discusses the possibility of participating in the study with the caregiver. ➤ If the caregiver is interested, the investigator presents and reviews the study informed consent form with the caregiver and reviews the information sheet with the child/adolescent. ➤ The caregiver voluntarily signs the study consent form. ➤ Subject ID is assigned. ➤ Subject is randomly assigned to Treatment Group. ➤ Study qualification inclusion/exclusion criteria evaluation is performed.
BASELINE ASSESSMENT

DEMOGRAPHICS AND TREATMENT HISTORY
 
 ➤ Demographic Variables recorded: gender, age, ethnicity ➤ Medication and Treatment History: Recording of all prescription and OTC medications used to date and therapies tried to date to treat autistic disorder or for any other indication 
BASELINE EVALUATION
 
 ➤ Aberrant Behavior Checklist (ABC) ➤ Clinical Global Impressions (CGI) Severity of Illness Scale (CGI-S) only
PROCEDURE ADMINISTRATION PHASE

GENERAL ASSESSMENT CONDITIONS
 
 ➤ Subject agrees to maintain his or her regular medication and dosage schedule to treat symptoms related to autism disorder throughout the study. ➤ Subject agrees to not change or start taking any new medications, or partake in any other new treatments, or to change the dosages they take of current medications, to treat the symptoms of autism disorder, during the course of study participation ➤ Subject agrees to notify the study investigator immediately if their treating physician makes any change to medication or dosage. ➤ Females of child-bearing age agree to use acceptable means of contraception throughout the study.

STUDY TREATMENT ADMINISTRATION PROTOCOL

The subject receives eight 5-minute study treatments with the Erchonia® HLS laser device: two treatments per week for 4 consecutive weeks, each treatment administration 3 to 4 days apart administered by the study investigator at the test site.

TREATMENT ADMINISTRATION PHASE: 4 WEEKS

AT EACH OF THE 8 STUDY TREATMENT ADMINISTRATION VISITS

- Medication and therapy use review
- Adverse events evaluation

WEEK 2 END: Study Midpoint

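### Random assignment comes before the eligibility check and baseline ratings, so children who fail are removed after assignment and the blocks balance consented rather than qualified children

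*Combined protocol and SAP*

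**What the plan says.** Two places set out the order of events, and they agree.

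- **Study Procedure Protocol, Pre-Treatment Activities.** The headings run: informed consent, subject identification number, Subject Group Randomization ("Subjects will be randomly assigned to either Treatment Group A or to Treatment Group B, following the methodology outlined above"), then the inclusion/exclusion evaluation with the DSM-IV-TR, ADI-R, ABC Irritability and CGI-S. The baseline assessment comes after that.
- **Table of Subject Events.** After consent and ID the next step is "Subject is randomly assigned to Treatment Group", then "Study qualification inclusion/exclusion criteria evaluation is performed", then demographics and the baseline ABC and CGI-S. The table is introduced with the words "The following table provides a progressive summary of subject events throughout the duration of this pivotal trial", so its order is meant as chronological.

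Other sections count differently. Under Subjects, a study subject is one of those "who pass the study qualification evaluation and are subsequently enrolled in the study". Under Subject Sample Size, "There will be 40 qualified subjects enrolled in this clinical study", and the rationale asks for "a minimum starting sample size of 20 subjects in each treatment group". Under Statistical Methods, "Subjects will be included in the ITT analysis if they complete their baseline clinical assessments and had at least one post-randomization efficacy evaluation".

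No section places randomisation after qualification. None says what happens to the allocation slot of an assigned child who then fails, or that such children are reported by group.

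**The concern.** A child who fails a criterion under this order has already been assigned to A or B and is then dropped. Three things follow.

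1. The blocks of two, four and six are balanced over everyone who consents. Removing some children leaves unplanned gaps, so the near-equal split that blocking should deliver among qualified children is lost.
2. The set called ITT leaves out randomised children for a reason that a different order would remove. Study success is declared on that set.
3. Eligibility, and the baseline ABC that becomes the ANCOVA covariate, are recorded after the letter is set. The ABC cut-off of 18 is numeric and the ADI-R is standardised, but the CGI-S rating and the presence of irritable behaviours call for judgement. If the person judging knew the letter, exclusion could come to depend on it.

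The third route is only partly closed. Under Double Blind Design only the administration investigator knows the letter, and that person is not told which letter is active. The plan does not say who judges eligibility, whether that person is masked to A/B, or when the letter is released. Subject Recruitment and Study Treatment Administration Protocol use the same investigator title for the recruiting physician and the person who treats. That does not show they are one person, but the wording does not separate them.

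**Working it through.** **The plan's own sample size.** Inputs from Rationale and Justification for Sample Size: difference 8.5, SD 8.9, two-sided 5%, power 80%.

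n per group = 2 × [8.9 × (1.960 + 0.842) / 8.5]² = 17.2, rounded up to 18. The stated 18 reproduces. Inflation: 18 / 0.89 = 20.2, stated as 20. The required number is not in dispute here.

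**Balance and accrual.** Simulation with permuted blocks of 2, 4 and 6 (assumed equally likely, since the plan does not say) and failure after assignment at rate f, independent of arm; 20,000 runs per rate. The documents give no failure rate, so f = 10, 20 and 30% are assumptions; f = 0 represents assignment after qualification. The first data row stops at 40 qualified children. The other rows continue until each arm has at least 20, which is the plan's stated minimum.

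| | f = 0 | 10% | 20% | 30% |
|---|---|---|---|---|
| Exactly 20/20 at 40 qualified | 80% | 37% | 27% | 23% |
| Mean qualified children beyond 40 to reach 20 per arm | 0.2 | 1.3 | 1.9 | 2.4 |
| 90th percentile of that excess | 1 | 3 | 5 | 6 |
| Mean randomised, then removed | 0 | 4.6 | 10.5 | 18.2 |

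The f = 0 figure is below 100% because the last block may be incomplete at the 40th child; the split is then at worst 21/19. A split of 22/18 or worse at 40 qualified never occurs at f = 0, and occurs in about 15, 29 and 39% of runs at the three assumed rates (a separate 8,000 runs per rate).

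Arithmetic check: stopping at 40 qualified, the expected number removed is 40f/(1 − f) = 4.4, 10.0 and 17.1. The table's counts are slightly higher because they run on until both arms reach 20.

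**Power.** Noncentral t, df = N − 3 (treatment plus one covariate), noncentrality = 8.5 / [8.9 × √(1/n₁ + 1/n₂)].

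- 20/20: noncentrality 3.02, power 83.7%
- 18/22: 3.01, power 83.3%
- 17/23: 2.99, power 82.8%

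**Type I error when exclusion is unrelated to arm.** With no treatment effect, 20 per arm and the same prognosis-based exclusion in both arms, 40,000 runs per setting give 4.9 to 5.1%.

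**Illustration only: exclusion that depends on arm.** Suppose the worst-prognosis fraction f is excluded in one arm and a random fraction f in the other, with correlation ρ between judged prognosis and adjusted change. With φ the standard normal density and z its quantile at 1 − f, bias = 8.9 × ρ × φ(z) / (1 − f):

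| f | Bias, ρ = 0.3 | Bias, ρ = 0.5 | Type I error, ρ = 0.3 / 0.5 |
|---|---|---|---|
| 10% | 0.52 | 0.87 | 5.6% / 6.1% |
| 20% | 0.93 | 1.56 | 6.3% / 8.7% |
| 30% | 1.33 | 2.21 | 7.4% / 12.1% |

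Bias is in ABC Irritability points. Every input except the SD is assumed, and nothing in the documents indicates that exclusion would depend on arm.

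**The case against.** The best case against rests on the plan's own safeguards and on the small numerical effect.

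- **Masking.** The sequence is concealed, the letter goes to one person who does not know what it means, and a separate masked investigator records the ABC and CGI, which also supply two of the eligibility thresholds. This stands as a real limit on bias. What remains open is that nothing assigns the eligibility judgement to that masked person or fixes when the letter is released.
- **Size.** Equal arms are not needed for the ANCOVA. If accrual runs until each arm has 20, no power is lost: a 20/22 split gives 85.4% by the same formula. This stands. The cost is then about one to two extra qualified children, plus children who are assigned and never treated.
- **Loose wording elsewhere.** Subject Privacy and Confidentiality says the ID is given on acceptance into the study, and Subject Recruitment item 4 goes from ID to qualification with no mention of randomisation. One could read these as placing assignment later. But item 4 also puts the ID before qualification, and neither place says when randomisation happens. They do not displace two explicit, agreeing sequences, though they should be reconciled with them.
- **The ITT definition.** Requiring a post-randomisation evaluation would drop some randomised children wherever randomisation sits. That is correct. Reordering removes only those who are ineligible or lack a baseline.
- **The bias illustration is constructed.** Agreed, and the conclusion does not use it.

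**Conclusion.** The concern holds and should be fixed. Both statements of the sequence put assignment before eligibility and baseline. Together with a sample defined as qualified children, this means removal after randomisation. At assumed failure rates of 10 to 30%, about 5 to 18 children would be assigned and then dropped, and an exact 20/20 split at 40 qualified falls from about 80% to between 37 and 23% of trials.

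The consequence for the primary test is small if exclusion is unrelated to arm: type I error stays near 5%, and power falls by less than one percentage point at 17/23. The case for change is that the order creates avoidable exclusions from the pivotal analysis set and leaves a judgement-based exclusion route that the text does not close, when a better order is free. The balance and removal figures depend on the assumed failure rates, on equal block-size probabilities and on failure independent of arm. The case report forms (Appendix C) were not available, so nothing is claimed about them.

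**What to change.** 1. In the Study Procedure Protocol and the Table of Subject Events, move randomisation to after eligibility is confirmed and the baseline ABC and CGI-S are recorded. Release the letter to the administration investigator only then, immediately before the first treatment.
2. State that eligibility is judged by someone masked to A/B. The existing assessment investigator could do this.
3. State that any child found ineligible after randomisation will be reported by group.
4. Align the wording on when the subject ID is assigned in Subject Privacy and Confidentiality and Subject Recruitment item 4 with this order.

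The cost is one step moved in two places, two added sentences and a small wording correction. No extra subjects, visits or staff are needed, and the sample size is unchanged.
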